## **2. RATIONALE, OBJECTIVES, AND BENEFIT - RISK ASSESSMENT**

### **2.1 RATIONALE FOR PERFORMING THE TRIAL**

As in other conditions where anticoagulation is required, warfarin has many challenges and risks associated with its use. These include among others numerous drug-drug interactions, drug-food interactions, risk of bleeding and the need of regular INR monitoring.

Thus, an alternative method of anticoagulation which can be taken orally, has fewer interactions and no regular monitoring requirement would be beneficial for the post-acute care of CVT patients. Dabigatran etexilate has a marketing authorisation for treatment of DVT and PE in many countries. The aetiology of CVT can be considered sufficiently similar to other VTE [[P10-00396](#), [R15-5862](#)] to consider treatment with the same dose of dabigatran etexilate as an alternative to standard treatment with VKA. Therefore, the selected dose of 150 mg b.i.d. is expected to be as efficacious as warfarin without the burden/disadvantages associated with that drug. It can be expected that the overall bleeding risk under dabigatran etexilate will be similar to that of warfarin or potentially better.

There is currently limited but promising clinical data on the use of dabigatran in this indication. Since the incidence of CVT is very low and the occurrence of clinical endpoints is infrequent, a large confirmatory phase III trial including clinical endpoints in this indication is not feasible. Although considered a phase III trial, this trial is not designed to show statistically significant differences in clinical endpoints and is not conducted for registration purposes. The trial is designed as an exploratory trial that could provide numerical reassurance regarding net clinical benefit of dabigatran etexilate compared to warfarin. A largely comparable percentage of clinical endpoints (VTE + MBEs according to International Society on Thrombosis and Haemostasis (ISTH) definition) for both treatment arms would provide clinicians with important new information.

### **2.2 TRIAL OBJECTIVES**

This is an exploratory trial to investigate the efficacy and safety of dabigatran etexilate versus dose-adjusted warfarin in patients with CVT after initial acute treatment.

The primary objective is to compare the net clinical benefit of the treatment arms, as measured by the composite of VTE (recurring CVT; DVT of any limb, PE, or splanchnic vein thrombosis) + major bleeding according to ISTH criteria after up to 24 weeks.

Secondary objectives include a comparison of additional efficacy and safety parameters.

## **2.3 BENEFIT - RISK ASSESSMENT**

At the time this protocol was prepared, the safety and efficacy of dabigatran etexilate had been evaluated in more than 27,000 patients in over 47 Phase I studies, nine completed Phase II studies, and 11 completed Phase III studies within multiple populations including:

- Venous thromboembolism (i.e. DVT and/or PE) prevention in patients who have undergone major orthopaedic surgery
- prevention of stroke and systemic embolism in patients with non-valvular AF
- acute treatment and secondary prevention of VTE (DVT and PE)

The most commonly reported adverse reactions of dabigatran etexilate are bleedings events. Although rare in frequency in clinical trials, major or severe bleeding may occur and, regardless of location, may lead to disabling, life-threatening or even fatal outcomes.

Standard management for bleeding (such as transfusion of blood products, etc.) needs to be applied as described in Section [4.2.1](#) and in Figure [4.2.1.1: 1](#). A specific reversal agent (idarucizumab) for dabigatran has been developed and is currently available in many countries and being reviewed for registration in various other countries. When clinically indicated and available, it can be given to a patient from commercial supply if it becomes locally approved. See Section [4.2.1.1](#) (Major Bleeds) for more information regarding the specific reversal agent for dabigatran.

The risk of major bleeding correlates with dabigatran plasma concentrations [[P13-12662](#)], but also depends on individual patient characteristics, such as age and renal function. Bleeding risk may also be higher in patients concomitantly treated with an antiplatelet agent, such as ASA or clopidogrel. Factors, such as decreased renal function (CrCl 30-50 mL/min), age  $\geq 75$  years, low body weight ( $< 50$  kg), or mild to moderate P-gp inhibitor co-medication (e.g. amiodarone, quinidine or verapamil) are associated with increased dabigatran plasma levels, thereby contributing to the overall risk of bleeding in an individual patient.

Major advantages of treatment with dabigatran etexilate lie in the greater convenience for the patient. Dabigatran etexilate does not require regular monitoring of the anticoagulant effect, and it has no food interactions, and few clinically relevant drug-drug interactions compared to VKA.

In addition, dabigatran etexilate has been shown to be associated with significantly less intracranial haemorrhage (ICH) compared to warfarin (relative risk reduction of 60-70%), which is seen irrespective of age and dosing .

In the CVT indication, the recommended warfarin dosing is identical to the warfarin dosing recommended for the SPAF indication and the acute treatment/secondary prevention of DVT/PE indications in which dabigatran etexilate was tested against warfarin. The recommended dosing of dabigatran etexilate for these indications (300 mg total daily dose) has therefore been chosen as the best equivalent for the CVT indication (see Section [4.1.3](#)).

Apart from the general considerations above, patient safety will be protected by recommendations provided in this clinical trial protocol. Patients may only be enrolled after stabilisation of the acute phase of the CVT. Patients participating in this clinical trial will be monitored throughout the course of the study for recovery from CVT and for any adverse effects of the trial medication.

Further safeguards that will be implemented to protect patient safety include:

- For both trial medications, the protocol includes guidance on handling haemorrhages which may occur in either treatment arm.
- In patients in the comparator arm (standard VKA treatment) plasma INR will be monitored and should be maintained between 2 and 3 to optimize efficacy and minimize risk of haemorrhage with VKA.
- Concerning the dabigatran etexilate treatment arm, similar efficacy to VKA is expected based on the mode of action of the drug and previous clinical trial experience in other indications.
- Medications which interact with dabigatran etexilate or warfarin are forbidden during the trial.
- Patients will undergo CrCl measurements at screening and patients with CrCl <30mL/min (at screening) will be excluded from participation to reduce the risk of bleeding when randomised to dabigatran etexilate; see Section [3.3.3](#) exclusion criteria.
- If a patient randomised to dabigatran etexilate experiences severe renal impairment (CrCl <30mL/min) during the study, study drug will be withheld or stopped (see Section [3.3.4.1](#) and Section [5.3.3](#)).
- Patients with a large volume of ICH will be excluded from this trial, by excluding patients that are planned for surgical treatment for CVT (e.g. decompressive surgery, ear-nose-throat surgery)
- Based on the findings on the nonclinical studies with dabigatran etexilate conducted to date and the available information for warfarin, and in accordance with international regulatory guidelines, the inclusion of women of childbearing potential (WOCBP) in this study is justified. To minimize the risk of unintentional exposure of an embryo or foetus to the investigational drug, WOCBP must agree to the requirements for pregnancy testing and contraceptive methods described in this protocol.
- Female patients are required to immediately contact the investigator if they experience signs and/or symptoms suggesting a potential pregnancy, or know that they are pregnant.
- A Data Monitoring Committee (DMC) will be established to monitor safety data of the study throughout the trial, and will recommend to the Sponsor (BI) whether to continue, modify or terminate the study (refer to Section [3.1.1](#) for details).

It is expected that this study will provide data that support the assumption that the net clinical benefit (composite of recurrent CVT/VTE and major ISTH bleeding) of dabigatran etexilate in CVT is similar to warfarin, with an overall lower risk of haemorrhage.

Proprietary confidential information © 2017 Boehringer Ingelheim International GmbH or one or more of its affiliated companies

Thus, the risk benefit assessment is considered favourable for the initiation and conduct of this trial.

### 3. DESCRIPTION OF DESIGN AND TRIAL POPULATION

#### 3.1 OVERALL TRIAL DESIGN AND PLAN

This is a phase III randomised, open label, exploratory trial with two parallel groups, with blinded endpoint adjudication (PROBE design, i.e. prospective, randomised, open-label, blinded endpoint).

Patients may be enrolled into the trial (i.e. sign informed consent) once they have a confirmed diagnosis of CVT and have received any required treatment for the acute phase of the illness as recommended by the AHA/ASA [R15-5005] and the European Federation of Neurological Societies (EFNS) [P10-11802]. This should include any treatment required for causal pathology or secondary symptoms, such as intracranial hypertension and must also include standard treatment with initial parenteral anticoagulation (UFH or LMWH) according to local treatment practice. Patients may have started oral anticoagulation with a VKA. After a short screening period patients should be randomised 5 to 15 days after start of UFH / LMWH (see Section 4.1.4 for details).

Patients will be randomised in a 1:1 ratio to receive either dabigatran etexilate (150 mg b.i.d.) or warfarin (dose adjusted to maintain an INR between 2.0 and 3.0).

[figure not shown]

Figure 3.1: 1 Study Design

### **3.1.1      Administrative structure of the trial**

A Coordinating Investigator will be nominated and will be responsible to coordinate investigators at different centres participating in this multicentre trial. Tasks and responsibilities will be defined in a contract. Relevant documentation on the participating (Principal) Investigators and other important participants, including their curricula vitae, will be filed in the Trial Master File (TMF).

A Steering Committee (SC) consisting of external (non-BI) experts and BI representatives has been established to support the Coordinating Investigator who will be the chair of the SC. The composition of the SC will be documented in the TMF. The tasks and responsibilities will be agreed in a SC-charter, which will be filed in the TMF.

A DMC, independent of the sponsor (BI) and of the SC, will be established to assess the progress of the clinical trial (including safety and efficacy assessment at specified intervals) and to recommend to the SC/sponsor whether to continue, modify, or stop the trial. The tasks and responsibilities of the DMC will be specified in a charter. The DMC will maintain written records of all its meetings.

An endpoint Adjudication Committee (AC), independent of the study sites and the SC, will be established for blinded adjudication of the following:

- VTEs
- MBE and CRNMBE
- Composite endpoint of new ICH or worsening of the haemorrhagic component of a previous lesion
- Cerebral venous recanalisation

The tasks and responsibilities of the AC will be specified in a charter.

BI has appointed a Trial Clinical Monitor (TCM), responsible for coordinating all required activities, in order to:

- manage the trial in accordance with applicable regulations and internal Standard Operating Procedures (SOPs),
- direct the clinical trial team in the preparation, conduct, and reporting of the trial,
- order the materials as needed for the trial,
- ensure appropriate training and information of local clinical monitors, Clinical Research Associates (CRAs), and Investigators of participating countries.

Data Management and Statistical evaluation, including programming, will be done according to BI SOPs.

Tasks and functions assigned in order to organise, manage, and evaluate the trial will be defined according to BI SOPs. A list of relevant responsible persons and relevant local contact information can be found in the ISF.

### **3.2 DISCUSSION OF TRIAL DESIGN, INCLUDING THE CHOICE OF CONTROL GROUP(S)**

Since VKAs are the standard of care for CVT, a controlled trial versus one such drug, warfarin, is considered appropriate. Dabigatran etexilate has been proven to be at least non-inferior in efficacy vs. warfarin in several trials of other indications, with fewer bleeding events as compared to warfarin, specifically less ICH .

Double-blind, double-dummy trials in anticoagulation have limitations due to potential unavoidable deviations from routine clinical procedures [[R08-4453](#)]. This exploratory trial will use the PROBE design (Prospective Randomised Open-label with Blinded Endpoint assessment). The PROBE approach has been used in several trials of anticoagulation comparing against VKA, e.g. in patients with atrial fibrillation.

In accordance with the applicable BI-SOP the trial database will be handled in a blinded way as appropriate until database lock; see also Section [4.1.5.1](#).

An independent DMC will ensure patient safety in case of a highly relevant difference in the efficacy or safety between the trial treatments. The trial duration is in line with current CVT treatment guidelines from AHA/ASA [[R15-5005](#)] and EFNS [[P10-11802](#)] and with the duration of anticoagulation trials conducted in DVT/PE.

The following procedures will be implemented to reduce the potential for bias in the reporting and assessment of primary and secondary events.

- Clearly defined objective outcomes:  
The primary and secondary outcomes of the study are clinically relevant events for which objective documentation will be obtained. Standard, widely accepted definitions are to be used that rely on objective documentation.
- Blinded AC:  
The events that make up the primary endpoint and the most relevant secondary endpoints will be adjudicated by blinded adjudication experts independent of the study sites and the SC. Blinding of all event documentation will be performed by trained specialists. The committee will report to the SC and the DMC.
- Review of Data for Clinical Events:  
Any Adverse Event (AE) indicative for a focal neurological deficit, such as limb weakness, loss of vision or sensory disturbance will trigger a request for more information from the centre for event adjudication if potentially consistent with a trial endpoint. Any decrease in haemoglobin of >2g/dL and any new VTE will be similarly investigated.

- **Data Handling:**

Patients will be randomly allocated to the treatment arms via Interactive Response Technology (IRT). Wherever feasible, data review and data handling will be undertaken without knowledge of patient treatment allocation. By treatment data tabulations will not be reviewed during the course of the trial.

By implementing these appropriate measures to avoid bias, the PROBE design is an acceptable and preferred approach for this study.

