### 5.3.5.2      Bleeding

All bleeding events that occur after signing of informed consent will be collected. Depending on the specific endpoint, events that occur after randomisation to trial medication or events that occur after first intake of trial medication will be part of the analysis of the bleeding events. See Section [7.3](#) for more details.

Patients should be carefully assessed for signs and symptoms of bleeding. Bleeding will be classified as major or minor. Major bleeds will be further sub-classified as fatal and other major bleeds. The location of the bleeding including the specific critical area or organ into which the bleeding occurred and whether or not it prolongs hospitalisation will be recorded. MBEs and CRNMBEs will be reviewed by the AC.

The following definitions are specified for bleeds:

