**Definition of a major bleed**

Major bleeds will be defined according to the ISTH definition of a major bleed, as follows [R05-0344]:

- Symptomatic bleeding in a critical area or organ, such as intracranial, intraspinal, intraocular, retroperitoneal, intra-articular or pericardial, or intramuscular with compartment syndrome

and/or

- Bleeding associated with a reduction in haemoglobin of at least 2g/dL (1.24mmol/L) within 24 hours, or leading to transfusion of two or more units of blood or packed cells

and/or

- Fatal bleed

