**Definition of a fatal bleeding**

Fatal bleeding is defined as a bleeding event that the AC determines as the primary cause of death or contributing directly to death.

 A seizure associated with a new intracranial bleed will be considered a symptomatic bleeding in a critical organ.

 Bleeding should be overt and the haemoglobin drop should be considered to be due to and temporally related to the bleeding event.

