## **7.7 DETERMINATION OF SAMPLE SIZE**

It is planned to randomise 60 patients per arm, resulting in 120 patients randomised in total. Assuming a drop-out rate of 10%, this should result in 108 evaluable patients (54 per treatment arm).

Due to the rare nature of the disease (CVT incidence of around 2 per 100.000 per year), and with limited availability of patients in this indication, the planned sample size in this trial is not based on any statistical considerations. No hypotheses will be tested or confirmed.

Data about recurrence rates for CVT patients are limited; Martinelli et al. [[R15-5570](#)] report a 5% recurrence rate after discontinuation of anticoagulation within the first year. We assume a 2-3% event rate for the composite primary endpoint with 6 months of treatment.

The trial is designed as exploratory; a comparable frequency for the primary endpoint between dabigatran and warfarin would provide clinicians with important new information.

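### At exactly 2.0 g/dL, the haemoglobin trigger for data review in protocol 3.2 does not match the major-bleed definition

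*Protocol*

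**What the plan says.** Protocol 3.2 introduces its list of safeguards with: "The following procedures will be implemented to reduce the potential for bias in the reporting and assessment of primary and secondary events". Under the item on review of data for clinical events, an adverse event pointing to a focal neurological deficit "will trigger a request for more information from the centre for event adjudication if potentially consistent with a trial endpoint". The next sentence extends this to laboratory falls: "Any decrease in haemoglobin of >2g/dL and any new VTE will be similarly investigated".

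The haemoglobin limb of the major-bleed definition in protocol 5.3.5.2 reads: "Bleeding associated with a reduction in haemoglobin of at least 2g/dL (1.24mmol/L) within 24 hours". SAP 5.1 repeats that threshold and time window. A footnote to the protocol definition adds: "Bleeding should be overt and the haemoglobin drop should be considered to be due to and temporally related to the bleeding event".

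On capture and adjudication, protocol 5.3.5.2 says: "All bleeding events that occur after signing of informed consent will be collected", and "MBEs and CRNMBEs will be reviewed by the AC".

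**The concern.** Investigators and patients know the allocation, and the protocol defends the open-label design by pointing to the safeguards in section 3.2. Blinded adjudication protects only the events that reach the committee. For bleeding, the haemoglobin trigger is the stated route to the committee that does not depend on how the unblinded site grades the event. It should therefore be at least as inclusive as the definition it serves.

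As written, it is not. A bleed with a fall of exactly 2.0 g/dL can meet the major-bleed definition, and so the primary endpoint, without prompting a query. If the site has graded that bleed as minor, no stated route takes it to the committee. A count in the primary endpoint and in the secondary endpoint of major bleeding would then rest on the site's grading alone.

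**Working it through.** The plan gives no figure to reproduce on this point. The check compares the two rules and then traces the routes to adjudication.

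**1. The threshold.** With haemoglobin recorded to 0.1 g/dL:

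| Fall (g/dL) | Trigger, 3.2 (more than 2) | Definition, 5.3.5.2 and SAP 5.1 (2 or more) |
|---|---|---|
| 1.9 | no | no |
| 2.0 | no | yes |
| 2.1 | yes | yes |

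The rules differ at one value. For sites reporting in mmol/L, take the definition's own equivalence of 2 g/dL to 1.24 mmol/L. On a 0.1 mmol/L grid, 1.2 fails both rules and 1.3 passes both, so there is no gap. On a 0.01 mmol/L grid only 1.24 falls in it.

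**2. The other conditions.** The trigger covers any decrease, with no time window and no bleeding condition. The definition requires the fall within 24 hours, from an overt bleed that caused it. In both respects the trigger is the wider rule.

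**3. Routes to the committee for an overt bleed with a 2.0 g/dL fall in 24 hours.**
- Reported by the site as a major bleed: adjudicated.
- Reported as clinically relevant non-major (it led to admission, to physician-guided treatment, or to a change, interruption or stop of trial medication): adjudicated.
- Another major criterion also met (critical site, transfusion of two or more units, fatal): the bleed qualifies as major without the haemoglobin limb.
- None of these, and graded minor by the site: collected as a bleeding event, but with no stated route to the committee. At 2.1 g/dL the trigger would have caught it.

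**4. Scale.** Protocol 7.7 says "It is planned to randomise 60 patients per arm, resulting in 120 patients randomised in total" and assumes a 2-3% primary event rate.
- Expected primary events: 120 x 0.02 = 2.4 to 120 x 0.03 = 3.6 in total, or 1.2 to 1.8 per arm.
- One event in an arm: 1/60 = 1.7 percentage points. This is the size of one miss if it happens, not the expected effect.

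**5. Illustration only.** The documents do not say how haemoglobin falls are distributed. Assume that qualifying falls spread evenly from 2.0 to 3.0 g/dL in 0.1 steps. That is 11 values, and the share at exactly 2.0 is 1/11, about 9%. The grid has to start at 2.0, since smaller falls do not qualify. Ending it at 2.5 or 4.0 instead gives 1/6 (17%) or 1/21 (5%), so the share is a product of the assumed range.

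Take the extreme case in which every expected primary event is a haemoglobin-only bleed that the site graded as minor. On the 1/11 share, missed events in the whole trial are 2.4/11 = 0.22 to 3.6/11 = 0.33, and 0.33/120 is about 0.3 percentage points. The real figure must be far lower, because the primary endpoint also includes venous thrombotic events and most routes in step 3 are open.

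**The case against.** The strongest reply is that the trigger is only a back-up. Bleeding is assessed at every visit, all bleeds are collected, and the clinically relevant non-major category is broad enough to carry most borderline bleeds to the blinded committee. After baseline, scheduled safety laboratory tests fall at Days 29, 85 and 169, and values weeks apart cannot establish a 24-hour fall. Two values within a day would normally be unscheduled tests that the site ordered, so the site would already know of the event. Section 3.2 is design rationale; the working rules for adjudication sit in a charter that is not among the documents and may already use the inclusive threshold. The trial is also descriptive and tests no hypothesis.

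Nearly all of this stands as an argument about size. It also rules out two readings that a reader might infer. One is that the trigger is narrower than the definition in general; it is narrower at one value and wider on timing and on the bleeding condition. The other is that bleeds with a 2.0 g/dL fall are lost to adjudication; those reported as major or clinically relevant non-major are not.

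The reply does not remove the mismatch. A site can know of a bleed and still grade it as minor, and that is the case a trigger independent of the site's grading exists to catch.

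**Conclusion.** The mismatch is real, stands in current text, and is minor. It matters only when every condition in the last route of step 3 holds. The expected effect on the primary endpoint is very small and cannot be estimated from the documents. The 9% share rests on an assumed distribution and should not be quoted as a finding.

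A reader might go further and infer that bleeds at the defining threshold are the ones most prone to different reporting between arms. Nothing in the documents supports that. They establish only that the site knows the allocation and that this one value lacks the trigger.

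The conclusion takes the inequality in section 3.2 literally and assumes that the unseen charter and data-review checks do not already use the definition's threshold. If they do, only an editorial inconsistency remains.

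**What to change.** In protocol 3.2, replace the strict inequality with a fall of at least 2 g/dL (1.24 mmol/L), matching protocol 5.3.5.2 and SAP 5.1. Leave the trigger without a time window or bleeding condition, since that breadth is useful in a screening rule. Confirm that the adjudication charter and the data-review checks apply the same threshold.

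The cost is a wording change at the next protocol amendment, a matching check setting if one is needed, and a few more queries to sites. Haemoglobin is already a safety laboratory parameter recorded in the CRF, so no new data are required. The endpoint definition, sample size and analyses do not change.
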